4.0 Sample size consideration

The sample size for Cohorts 1 and 2 is based on: 1) dose de-escalation rules and 2) the number of subjects required to detect moderate to large increases in ORR relative to historical control with sufficient power while constraining Type I error to 0.10. This study is expected to require 45 subjects, 6 subjects evaluated for safety in each cohort and an additional 20 and 13 subjects enrolled in Cohorts 1 and 2, respectively. More subjects may be enrolled if de-escalation of dose levels is indicated in the safety evaluation.

The sample size of 12 subjects each for Cohorts 3 and 4 is chosen to provide evaluation for safety and tolerability.

Cohorts 1 and 2

Each of Cohorts 1 and 2 are expanded at the recommended dose level to include, respectively, 26 and 19 total relapsed/refractory and treatment-naïve CLL subjects. These sample sizes were chosen to obtain sufficient preliminary safety and efficacy information in these populations. With respect to toxicity and ability to detect common adverse events (AEs), there is an approximately 60% chance of observing at least 1 subject with an AE occurring at a 5% rate with 19 treatment-naïve subjects in Cohort 2 and an approximately 75% chance in the group of 26 relapsed/refractory CLL subjects in Cohort 1.

If toxicity profiles are similar and it is appropriate to summarize AEs across all subjects, there is at least a 90% chance of detecting a common AE. With respect to clinical efficacy, a 50% ORR (partial response with lymphocytosis or better) (null) at the 12-month evaluation would be considered uninteresting because this can be achieved with either acalabrutinib or obinutuzumab as single agents in both populations. However, an ORR of at least 75% in the relapsed/refractory setting for Cohort 2 and an ORR of at least 80% in the treatment-naïve setting for Cohort 1 would be of considerable interest and would warrant further investigation of the combination regimen (alternative).

If 16 or fewer responses are observed in 26 evaluable subjects with relapsed/refractory CLL in Cohort 1, the combination of acalabrutinib with obinutuzumab would not be considered promising; likewise, if 12 or fewer responses in 19 evaluable subjects who were previously untreated for CLL in Cohort 2 were observed, the combination would not be considered promising as upfront therapy. Each of these designs has at least 90% power with a one-sided alpha level of 0.10.

Cohorts 3 and 4

The sample sizes for Cohorts 3 and 4 are chosen to obtain preliminary safety information in the relapsed/refractory and treatment-naïve CLL populations. With respect to toxicity and ability to detect common AEs, there is a 46% chance of observing at least 1 subject with an AE occurring at a 5% rate with 12 subjects in each of Cohorts 3 and 4.

Below is a list of various AE rates with the chance of observing in at least 1 subject.

Sample Size	Adverse Event Rate	Chance of Observing at Least 1 Adverse Event
12	1%	11%
12	2%	22%
12	5%	46%
12	10%	72%

5.0 Analysis POPULATIONS

Analysis populations will be defined in the following sections. The efficacy and safety analyses will be performed on the All Treated Population. The primary efficacy analysis will be based on the Efficacy Evaluable Population.

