14.4 Statistical Design

Cohorts 1 and 2 will use a Phase 1b study design with de-escalation to determine a safe and tolerable dose level to be recommended for the expansion portion. [Section 6.5](#) provides the details of the study design for dose finding. Each of Cohorts 1 and 2 will be expanded at the recommended dose level to include, respectively, 26 and 19 total relapsed/refractory and treatment-naive CLL subjects. These sample sizes were chosen to obtain sufficient preliminary safety and efficacy information in these populations. With respect to toxicity and ability to detect common AEs, there is approximately a 60% chance of observing at least 1 subject with an AE occurring at a 5% rate with 19 treatment-naive subjects in Cohort 2, and approximately a 75% chance in the group of 26 relapsed/refractory CLL subjects in Cohort 1. If toxicity profiles are similar and it is appropriate to summarize AEs across all subjects, there is at least a 90% chance of detecting a common AE. With respect to clinical efficacy, a 50% ORR (PRL or better) (null) at the 12-month evaluation would be considered uninteresting as this can be achieved with either of acalabrutinib or obinutuzumab as single agents in both populations. However, an ORR of at least 75% in the relapsed/refractory setting for Cohort 2 and an ORR of at least 80% in the treatment-naive setting for Cohort 1 would be of considerable interest and would warrant further investigation of the combination regimen (alternative). If 16 or fewer responses are observed in 26 evaluable subjects with relapsed/refractory CLL in Cohort 1, the combination of acalabrutinib with obinutuzumab would not be considered promising; likewise, if 12 or fewer responses in 19 evaluable subjects who were previously untreated for CLL in Cohort 2 were observed, the combination would not be considered promising as upfront therapy. Each of these designs has at least 90% power with a 1-sided alpha level of 0.10.

The sample sizes for Cohorts 3 and 4 are chosen to obtain preliminary safety information in the relapsed/refractory and treatment-naive CLL populations. With respect to toxicity and ability to detect common AEs, there is a 46% chance of observing at least 1 subject with an AE occurring at a 5% rate with 12 subjects in each of Cohort 3 and 4. Below is a list of various AE rates with the chance of observing at least 1 subject with that AE.

Sample Size	Adverse Event Rate	Chance of Observing at Least 1 Adverse Event
12	1%	11%

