12	2%	22%
12	5%	46%
12	10%	72%

14.5 Analysis Populations:

- All-treated Population: All enrolled subjects who receive ≥ 1 dose of study drug. The All-treated Population will be used for the efficacy and safety analyses.
- Efficacy-evaluable Population: All subjects in the All-treated Population who have ≥ 1 evaluable response assessment after the first dose of study drug. The Efficacy-evaluable Population will be used for sensitivity analysis.

For Cohorts 1 and 2, if in the DLT observation portion, a subject discontinues study prior to completing the second cycle of treatment at a dose level for reasons other than toxicity, an additional subject may be enrolled at that dose level for purposes of the DLT assessment and decision rules.

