7.4 Missing Data Handling

No imputation for missing values of efficacy endpoints. Imputation for missing dates such as AE start or end dates and prior and concomitant medication start dates or end dates will be documented in the programming specifications.

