12.0 Efficacy analyses

Response will be assessed by investigators based on International Workshop on Chronic Lymphocytic Leukemia (IWCLL) Response Assessment Criteria (modified from Hallek 2008) with incorporation of the clarification for treatment-related lymphocytosis per Cheson 2012 for CLL/SLL.

The efficacy analysis will be performed using All Treated Population. The Efficacy Evaluable Population will be used for primary efficacy analysis.

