12.1 Primary Efficacy Endpoint and Analysis

12.1.1 Overall Response Rate (ORR)

ORR is the proportion of subjects who achieve complete remission (CR), CR with incomplete bone marrow recovery (CRI), nodular partial remission(nPR), or partial remission (PR) while on treatment before the initiation of new anticancer therapy or stem cell transplant.

For Cohorts 1 and 2, the ORR(PR or better) at the all available response assessments up to the 12-months will be calculated and 95% exact binomial CIs will be provided.

ORR will be summarized using All Treated Population and Efficacy Evaluable Population.

For CLL disease subgroups, ORR, including PRL as a response, (only for Cohorts 1 and 2), will also be summarized in the same fashion.

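### The SAP makes the Efficacy Evaluable set primary for the Cohort 1 and 2 ORR, against Protocol 14.5, so the headline ORR can only rise or stay the same

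*SAP*

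**What the plan says.** Protocol 14.5 defines two sets and gives each a role. On the first: "The All-treated Population will be used for the efficacy and safety analyses". On the second: "The Efficacy-evaluable Population will be used for sensitivity analysis".

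The SAP changes those roles for the primary endpoint. SAP 5.0 says "The primary efficacy analysis will be based on the Efficacy Evaluable Population", and SAP 12.0 repeats it: "The Efficacy Evaluable Population will be used for primary efficacy analysis". In both places an adjacent sentence assigns efficacy generally to All Treated, and SAP 12.2 uses All Treated for the secondary efficacy endpoints. SAP 5.2 admits a treated subject to the evaluable set if there was at least one response assessment after the first dose.

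Three other places bear on the point:

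- SAP 12.1.1 plans both tables: "ORR will be summarized using All Treated Population and Efficacy Evaluable Population".
- SAP 7.4 says "No imputation for missing values of efficacy endpoints". Nowhere do the documents state that a treated subject without an assessment counts as a non-responder.
- The decision rule speaks of evaluable subjects. Protocol 14.4 has "If 16 or fewer responses are observed in 26 evaluable subjects with relapsed/refractory CLL in Cohort 1", and SAP 4.0 has "if 12 or fewer responses in 19 evaluable subjects who were previously untreated for CLL in Cohort 2 were observed". Yet 26 and 19 are the full planned sizes of the two cohorts.

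**The concern.** The SAP presents itself as detailing the analyses of Protocol Amendment 7. SAP 1.0 describes what was updated, and a change of primary population is not among the updates. The departure is unexplained, and it runs in the favourable direction.

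Subjects who progress early or stop for toxicity will mostly have some post-dose assessment, through the progression visit or discontinuation follow-up, and so stay in. Those likely to drop out of the primary denominator are early deaths, losses to follow-up, consent withdrawals, and subjects who deteriorate symptomatically and are not assessed again. Protocol 8.4 exempts the first three from continued follow-up, and Protocol 10.3 lets the investigator forgo further disease assessment in the last. The first scheduled tumour assessment is at Day 85 (SAP Appendix A), which leaves time for such losses. The PFS censoring table in SAP 12.2.3 already has a row for subjects with no adequate post-baseline assessment.

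SAP 7.1 plans no formal hypothesis tests, so the estimate and its interval are the primary result. With cohorts of 26 and 19, one or two subjects in the denominator matter.

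**Working it through.** **Inputs.** Planned sizes N = 26 (Cohort 1) and N = 19 (Cohort 2); promising if at least 17 or at least 13 respond; null ORR 50%; targets 75% (relapsed/refractory) and 80% (treatment-naive); one-sided alpha 0.10 and at least 90% power (Protocol 14.4, SAP 4.0). Intervals are exact binomial 95% (SAP 12.1.1). The number of treated subjects with no assessment, k, is not given; k = 0 to 4 is an assumption.

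**1. The plan's own figures.** With X binomial:

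- N = 26: P(X ≥ 17 | 0.50) = 0.084; P(X ≥ 17 | 0.75) = 0.909.
- N = 19: P(X ≥ 13 | 0.50) = 0.084; P(X ≥ 13 | 0.80) = 0.932.

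Both meet the stated alpha and power, using the full cohort sizes.

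**2. Direction.** Let x be the number of responders. Being a responder requires an assessment, so all k excluded subjects are non-responders. All Treated gives x/N; Efficacy Evaluable gives x/(N − k), which is never smaller. The exact limits were checked for every x and k at N = 26 and N = 19: neither limit ever fell.

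**3. Size at the smallest promising count.**

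| k | Cohort 1, x = 17 | Cohort 2, x = 13 |
|---|---|---|
| 0 | 17/26 = 65.4% (44.3–82.8) | 13/19 = 68.4% (43.4–87.4) |
| 1 | 17/25 = 68.0% (46.5–85.1) | 13/18 = 72.2% (46.5–90.3) |
| 2 | 17/24 = 70.8% (48.9–87.4) | 13/17 = 76.5% (50.1–93.2) |
| 3 | 17/23 = 73.9% (51.6–89.8) | 13/16 = 81.3% (54.4–96.0) |
| 4 | 17/22 = 77.3% (54.6–92.2) | 13/15 = 86.7% (59.5–98.3) |

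**4. How the interval reads against 50%.** One response above each cut-off, a single exclusion moves the lower 95% limit across 50%: 18/26 gives 48.2% and 18/25 gives 50.6%; 14/19 gives 48.8% and 14/18 gives 52.4%.

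**5. The count rule.** Suppose the true All-treated ORR is 50% and the excluded subjects are all non-responders. The rate among those left is 0.5N/(N − k). At k = 2 this is 13/24 = 0.542 and 9.5/17 = 0.559. The chance of reaching the fixed cut-off is then:

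- Cohort 1: P(X ≥ 17 | n = 24, 0.542) = 7.4%, against 8.4% at k = 0.
- Cohort 2: P(X ≥ 13 | n = 17, 0.559) = 6.9%, against 8.4% at k = 0.

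Applied as written, the rule does not become easier to pass.

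**The case against.** The strongest reply is that this is a labelling mismatch with little practical effect. Both ORR tables are planned, SAP 8.0 already reports how many subjects fall in each population, and the go/no-go rule is a count. All of that stands, and it limits the harm to which estimate is headlined.

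k may also be small. One assessment at any time after the first dose is enough to stay in, and the SAP omits the Protocol's requirement that the assessment be evaluable, so its set is at least as large as the Protocol's. At k = 1 the shift is 2.6 points in Cohort 1 and 3.8 in Cohort 2; k = 4 would mean 21% of Cohort 2 was never assessed. This is fair: the upper rows of k show a range and are not a forecast.

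The crossing of 50% is not the design's criterion. 18/26 and 14/19 already pass the count rule, with one-sided exact p of 0.038 and 0.032, and the 50% null is set for PRL or better while the primary ORR counts PR or better. That too is correct. The crossing shows how a reader might see the interval; no planned decision changes.

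The ORR definition in SAP 12.1.1 arguably already treats an unassessed subject in the All Treated table as not having responded. An explicit sentence would still remove doubt, given SAP 7.4.

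Finally, the decision rule itself says *evaluable*, and the SAP may be following it. But its denominators equal the full cohorts, and Protocol 14.5 is where populations are expressly assigned. The wording may explain the SAP's choice, but it does not settle the conflict in the SAP's favour.

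**Conclusion.** The concern holds. The SAP names a different primary population from the Protocol for the Cohort 1 and 2 ORR, without a reason, and the change can move the headline ORR and its interval only upward or not at all. At the smallest promising counts the rise is 5.4 points in Cohort 1 (70.8 − 65.4) and 8.1 points in Cohort 2 (76.5 − 68.4) if two subjects in each cohort were never assessed, and zero if all were. The direction rests only on the fact that an unassessed subject cannot be a responder; the size rests on the assumed k. The false-promising rate of the stated cut-offs does not increase. This should be fixed before the ORR is reported, but it does not undermine the design.

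**What to change.** - **SAP 5.0 and 12.0:** name All Treated as the primary population for ORR.
- **SAP 12.1.1:** state that treated subjects with no response assessment count as non-responders, and cross-refer to this from SAP 7.4. Keep the Efficacy Evaluable table already planned there, labelled as the sensitivity analysis, and report k with reasons by cohort.
- **SAP 4.0:** say that the 17/26 and 13/19 rule applies to treated subjects.
- **Protocol 14.4:** align the word *evaluable* at the next amendment.

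Amending and justifying Protocol 14.5 instead would also reconcile the documents, but it would leave the one-directional shift in the primary estimate.

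The cost is wording in five SAP sections and one minor Protocol edit, which needs IRB approval as part of an amendment (Protocol 15.3). No new data or tables are needed. The headline ORR may be slightly lower.

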5.1 All Treated Population

The All Treated Population will include all enrolled subjects who received ≥ 1 dose of study drug.

All enrolled subjects were treated with at least one dose of study drug in this study, thus all-treated population is the same as the enrolled population.

5.2 Efficacy Evaluable Population

The Efficacy Evaluable Population will include all subjects in the All Treated Population who had ≥ 1 response assessment after the first dose of study drug.

6.0 TREATMENTS AND MEDICATIONS

6.1 Prior Anticancer Therapies

A prior anticancer therapy is defined as a systemic therapy subjects received, either as a single or combination therapy, for the treatment of active CLL/SLL with an end date occurring before the date of first dose of study treatment. Therapies given as a consolidation or maintenance of a response or remission will not be considered as a separate regimen. The number of prior therapies, type of prior therapy, and time (months) from the end of last therapy to the first dose of study drug will be summarized.

6.2 Prior and Concomitant Medications

Prior and concomitant medications will be coded according to the World Health Organization (WHO) drug dictionary. Medications started or ended prior to first dose will be considered as prior medications. Concomitant medication is defined as all medications used on or after the first dose, through the treatment phase, and for 30 days following the last dose of study drug. With use of this definition, a medication can be classified as both prior and concomitant. Medications with completely missing start and stop dates will be considered as both prior and concomitant medications.

[Appendix D](#) shows the prior and concomitant medication flags for various scenarios. The number and percentage of subjects will be presented by anatomical therapeutic chemical (ATC) classification system Level 2 and preferred term.

Prior and concomitant medications will be summarized by the WHO drug dictionary Anatomical Therapeutic Chemical (ATC) level 2 and preferred term (PT).

6.3 Study Treatment Exposure

Study treatment exposure will be summarized for all subjects in the Safety population. The following will be provided for each treatment component when applicable:

- Duration of exposure
 - Acalabrutinib and venetoclax (months): (last dose date – first dose date + 1) / 30.4375
 - Obinutuzumab and rituximab (days): (last dose date – first dose date + 28)
- Cumulative dose received on study (acalabrutinib, venetoclax, rituximab, and obinutuzumab)
- Average daily dose (acalabrutinib and venetoclax only)
 - Calculated as (total dose received [mg] / duration of exposure [days])
- Relative dose intensity
 - Acalabrutinib:
 - Calculated as (total cumulative dose received [mg] / (duration of exposure [days] * 100 [mg] * 2) *100)
 - Obinutuzumab:
 - Calculated as (total volume infused (mg) / 8000 mg * 100)
 - Rituximab:
 - Calculated as (total dose infused [mg] / total cumulative planned dose based on body surface area [375 mg/m²] * 100)
 - Venetoclax:
 - Calculated as (total cumulative dose received [mg] / 136,990 mg * 100)
- Dose withholding
 - Acalabrutinib: missing dose for \geq 7 consecutive days
 - Venetoclax, Obinutuzumab, Rituximab : missing dose for at least 1 day
- Dose reduction
 - Acalabrutinib: taking lower dose level for \geq 3 consecutive days
 - Venetoclax, Obinutuzumab, Rituximab: taking lower dose level for at least 1 day
- Infusion interruption (Obinutuzumab and Rituximab only)

- Time to first interruption (days) (Obinutuzumab and Rituximab only)

7.0 Statistical Methods

7.1 Data Presentation

Tables and figures will be summarized by cohort unless otherwise specified.

No formal tests of hypotheses will be performed. P-values, if presented, will be provided for descriptive purpose. Descriptive statistics (number of subjects, mean, and standard deviation, median, minimum, and maximum) will be presented for continuous variables, including baseline demographic, disease characteristics, study drug administration, efficacy and safety outcomes. Categorical variables will be summarized as the number and percentage of subjects per category. Confidence intervals [CIs] may be included as appropriate.

7.2 General Conventions

Baseline is defined as the last measurement taken prior to the first dose of study drug administration. Post-baseline is defined as a measurement taken after the first dose of study drug administration.

Study Day 1 is defined as the date of first dose. For visits (or events) that occur on or after first dose date, study day is calculated as (date of visit [event] – date of first dose + 1). For visits (or events) that occur prior to first dose date, study day is calculated as (date of visit [event] – date of first dose). There is no Study Day 0.

Laboratory data summary will be based on central laboratory results. Local laboratory results will be used if central laboratory results are not available. Central laboratory results will use reference ranges provided by the central laboratory, and local laboratory results will use the reference ranges provided by local laboratories.

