8.4 Discontinuation Follow-up

After discontinuation of study treatment for any reason (except for death, lost to follow up, or withdrawal of consent), each subject should be followed until disease progression. If disease progression has not occurred at the time of the 30-day SFU visit, discontinuation follow-up visits should occur approximately every 12 weeks until disease progression. During this period, subjects will be followed via CT scans (every 24 weeks), CBC with differential, physical examinations (including vital signs and weight), serum chemistry, peripheral blood MRD (every 6 months for subjects in Cohorts 3 and 4 who will be monitored while off study drugs), and bone marrow biopsy and aspirate (as clinically indicated); after 2 years in discontinuation follow-up, CT scans will be yearly. Refer to the Schedule of Assessments ([Section 8](#)) for a full list of assessments required during this period.

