10.2 Monitoring of Adverse Events

After the signing of the Informed Consent Form (ICF) and prior to the first dose of study drug, all SAEs must be reported.

After the first dose of study drug, all AEs/SAEs, irrespective of attribution of causality, must be reported.

All AEs will be reported until 30 days after the last dose of study drug(s) or the start of a new anticancer therapy (whichever comes first). After this period, investigators should report SAEs or other AEs of concern that are believed to be related to prior treatment with study drug.

All SAEs that occur during the reporting period should be followed to resolution or until the investigator assesses the subject as stable, or the subject is lost to follow-up or withdraws consent. Resolution/stable means the subject has returned to baseline state of health or the investigator does not expect any further improvement or worsening of the event.

The events must be detailed to include diagnostic term, severity, causality in relationship to the study drug, duration, action taken and outcome. The descriptions and grading scales found in the NCI-CTCAE version 4.03 or higher will be utilized for AE reporting.

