13.1 Adverse Events

AEs will be coded using the Medical Dictionary for Regulatory Activities (MedDRA v 24.0) reporting system. The investigator will grade AEs according to the National Cancer Institute Common Terminology Criteria for Adverse Events (NCI-CTCAE) v4.03 for AEs.

Hematologic toxicity is assessed by the investigator according to IWCLL 2008 guidelines for Cohorts 1 and 2, and NCI CTCAE v4.03 for Cohorts 3 and 4. TEAEs are defined as those events that occur on or after the first dose of study drug, through the treatment phase, and within 30 days following the last dose of study drug.

All TEAEs will be summarized by cohort as treated. For each cohort, AE incidence rates will be summarized with frequency and percentage by system organ class and preferred term, and the denominator for the AE incidence rate will be based on the number of subjects treated in that cohort unless otherwise specified. In addition, AE incidence rates will also be summarized by severity, and relationship to study drug. Relationship to study drug, per the investigator's judgment, is recorded on the CRF.

Subjects with multiple occurrences of events for a given preferred term, system organ class, or overall will be counted only once at the maximum severity, and strongest relationship to study drug for each preferred term, system organ class, and overall, respectively.

Summaries will be presented for:

- treatment-emergent AEs
- treatment-emergent serious adverse events (TESAEs)
- treatment-related TEAEs
- treatment-related TESAEs
- AEs leading to study drug discontinuation or dose modifications or dose delay
- treatment-emergent fatal (Grade 5) AEs

13.2 Adverse Events of Clinical Interest.

Adverse events of clinical interest (ECIs) are specified in Appendix F. Subject incidence rates of AEs of clinical interest will be summarized similarly to TEAEs by cohort.

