13.4 Laboratory Assessments

13.4.1 Data Summary Methods

All laboratory values will be converted to and reported as SI units and classified as normal, low, or high based on the normal ranges provided by the local laboratory.

Hematologic parameters, including platelet counts, hemoglobin, and neutrophils, will be summarized by IWCLL 2008 ([Appendix C](#)) and NCI CTCAE v4.03 respectively. All other gradable laboratory parameters will be graded using the NCI CTCAE v4.03.

Per the grading scale in the IWCLL guidelines, ANC: Both baseline grade and post-baseline grade are defined based on absolute values and 2) Hemoglobin and platelet: baseline grade is not applicable (no criterion is provided to define baseline grade) and post-baseline grade is based on percentage decrease from baseline value.

Gradable parameters that have criteria available for both low and high values (e.g., hypercalcaemia for a high value of calcium and hypocalcaemia for a low value of calcium) based on the NCI CTCAE v4.03 will be summarized for both criteria (low and high).

Subjects will be counted only once for each criterion/direction. The same subject can be counted for both criteria if the subject has laboratory values meeting each criterion. Subjects meeting the criteria for Grade 1 or higher for the high direction will be summarized under Grade 0 when summarizing the low direction and vice versa.

For each laboratory parameter, the baseline laboratory value/grade is defined as the last laboratory value/grade collected on or prior to the date of the first dose of study drug. The change from baseline to post-baseline value will be calculated for each parameter.

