13.4.2 T/B/NK Cell Counts

Descriptive statistics will be presented at baseline, last post-baseline, minimum post-baseline, and maximum post-baseline for the flow cytometry testing parameters (CD3⁺, CD4⁺, CD8⁺, , CD19⁺, and NK cells).

Changes from baseline at each of the last, minimum, and maximum post-baseline time points will be summarized. Figures will be presented for the mean of selected parameters over time as appropriate.

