13.6 ECOG Performance Status

Shift of ECOG from baseline to the worst score during the treatment will be summarized in a shift table.

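### SAP 7.2 gives the post-baseline period no end, so worst laboratory grades and last/minimum/maximum safety values can include off-treatment results

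*SAP*

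**What the plan says.** SAP 7.2: "Post-baseline is defined as a measurement taken after the first dose of study drug administration". No end is given there, and the later sections that use the term add none:

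- SAP 13.4.1, IWCLL grading of hemoglobin and platelets: "post-baseline grade is based on percentage decrease from baseline value".
- SAP 13.4.2, T/B/NK cells: "Changes from baseline at each of the last, minimum, and maximum post-baseline time points will be summarized". Sections 13.4.3 (immunoglobulins) and 13.5 (vital signs) summarize the same three values.

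Other safety outputs in the same SAP are bounded. Section 13.1 limits TEAEs to events "on or after the first dose of study drug, through the treatment phase, and within 30 days following the last dose of study drug". Section 13.6 reports "Shift of ECOG from baseline to the worst score during the treatment", and the blood-pressure shift in 13.5 is likewise limited to treatment.

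On data collection, Protocol 8.4 says that after discontinuation "subjects will be followed via CT scans (every 24 weeks), CBC with differential, physical examinations (including vital signs and weight), serum chemistry", at visits about every 12 weeks until progression. Off-drug follow-up is foreseen. Cohort 1 and 2 subjects in bone marrow MRD-negative CR may stop acalabrutinib (Protocol 6.1.1, 6.7). Cohort 3 and 4 subjects in CR, CRi and/or MRD negativity may stop after Cycle 24 (Tables 12 and 13, footnote A).

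**The concern.** A worst grade, a minimum and a maximum are each taken over all eligible records. If eligibility never ends, a hemoglobin or platelet fall caused by CLL returning after the drug was stopped is graded in the same table as treatment toxicity. For a subject in long discontinuation follow-up, the last vital-sign value is an off-drug value.

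Safety is the primary objective in Cohorts 3 and 4 and one of the primary objectives in Cohorts 1 and 2. The laboratory tables would describe a different period from the TEAE tables beside them, and nothing in the output would show it.

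**Working it through.** The plan states no figure to reproduce, because the issue is a rule for including data. The check has four parts.

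**1. Does anything else close the period?** SAP 7.3 assigns results to visits by date, and the Appendix A windows run on study day whether or not the subject is on drug. The last hematology/chemistry window (C36D1) starts at Day 856 and has no upper limit. No other SAP section supplies a cut-off.

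**2. What would be included?** This is an illustration for a subject who stops acalabrutinib at the end of Cycle 24, assuming no other study drug is given later and no progression.

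- Cycle length is 28 days, from Appendix A: C24D1 = 1 + 28 × 23 = Day 645.
- Last dose: 28 × 24 = Day 672.
- Last dose + 30 days: Day 702.
- Visits every 84 days counted from Day 702: Days 786, 870, 954, 1038 and so on.
- Two years after last dose is 672 + 730 = Day 1402, and (1402 − 702)/84 = 8.3. So 8 off-drug visits fall within two years, the last at 702 + 8 × 84 = Day 1374.
- Under Appendix A, the Day 786 result is labelled C30D1 (688–855), and every result from Day 870 is labelled C36D1.

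The windows therefore give off-drug values on-study visit labels and do not exclude them.

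**3. Which tests and cohorts?**

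- *CBC, chemistry, vital signs.* Protocol 8.4 lists them for discontinuation follow-up without limiting them to particular cohorts. For Cohorts 1 and 2, however, Table 11 marks no CBC or Chem 10 in that column and has no vital-signs row. The two places conflict and must be reconciled.
- *T/B/NK flow.* It is not scheduled in discontinuation follow-up in any cohort. After the safety follow-up visit it appears only at relapse (Tables 11, 12, 13).
- *Immunoglobulins.* They are scheduled no later than the safety follow-up visit in all three tables, at 30 (+7) days after last dose.
- *Values under later therapy.* Table 11 footnote J ends Cohort 1 and 2 discontinuation follow-up at alternative anticancer therapy. Section 8.4 and footnote I of Tables 12 and 13 name only progression, so in Cohorts 3 and 4 sampling can continue under a new treatment. In all cohorts Protocol 8.3 keeps the safety follow-up visit after new therapy.

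**4. Direction and unit of effect.** Adding records cannot lower a worst grade or a maximum and cannot raise a minimum; the last value can move either way. One reclassified subject changes a cohort rate by:

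- Cohort 3 or 4: 100/12 = 8.3 points
- Cohort 2: 100/19 = 5.3 points
- Cohort 1: 100/26 = 3.8 points

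**The case against.** The strongest reply is that these are supplementary descriptive tables. SAP 7.1 plans no formal tests, and the adverse-event summaries, including investigator-assessed hematologic toxicity, are already bounded: "through the treatment phase, and within 30 days following the last dose of study drug". That stands. A reader might infer that the TEAE results are biased upward; they are not affected.

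Second, acalabrutinib by default continues to progression. For a subject who progresses on drug, the relapse sample usually falls on treatment or within 30 days of last dose and would stay in the table under any sensible cut-off. That also stands. Only relapses in subjects who had already stopped are at issue, and stopping is optional.

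Third, the schedules limit the reach. It is tempting to say that last immunoglobulin values mix depletion with late recovery, or that neutropenia under the next regimen is counted in every cohort. The collection schedules and footnote J do not support either statement.

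Fourth, one could assume a Grade 3 rate per off-drug panel and multiply it over several years. The documents give no such rate and no number of subjects stopping electively, and repeated panels in one subject are not independent. SAP 13.4.1 counts a subject once per criterion and direction, so someone already at that grade on treatment adds nothing. Such a figure would not measure the change in the table.

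None of this supplies the missing end date. The SAP states a definition, and applying it as written admits off-treatment values.

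**Conclusion.** The concern holds in a limited form. As written, SAP 7.2 lets off-drug results, including those at off-drug relapse, into the laboratory-grade tables and the last/minimum/maximum summaries.

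- Clearest: CBC, chemistry and vital signs in Cohorts 3 and 4.
- Conditional: the same tests in Cohort 1 and 2 discontinuation follow-up, if Section 8.4 prevails over Table 11.
- Also affected: T/B/NK values at off-drug relapse.
- Largely confined to Cohorts 3 and 4: values under later therapy.
- Little affected: immunoglobulins.
- Not affected: TEAE tables.

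The overall size is unknown. It depends on how many subjects stop before progression, how long they are followed, and how often an off-drug value is worse than the worst on-drug value. In cohorts of 12 to 26, a single such subject is visible in a rate.

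**What to change.** In SAP 7.2, add an on-treatment post-baseline period for Sections 13.4.1 to 13.4.3 and 13.5. It runs from after the first dose through 30 days after the last dose of any study drug, or to the start of new anticancer therapy if earlier. State that the safety follow-up visit, allowed to day 37, is included.

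The stop at new therapy follows Protocol 10.2: "All AEs will be reported until 30 days after the last dose of study drug(s) or the start of a new anticancer therapy". There the earlier of the two dates applies. The TEAE window in SAP 13.1 lacks that stop, so apply the same end rule there; otherwise the laboratory and adverse-event tables still will not reconcile.

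Show later values in a separate off-treatment table or listing so that late cytopenias stay visible. Leave the efficacy derivations unchanged. Reconcile Protocol 8.4 with Table 11 on what is collected in Cohort 1 and 2 discontinuation follow-up.

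The cost is a short SAP edit, one record-level flag and one extra output. The small downside is that late laboratory abnormalities move from the main table to a separate one.
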